5. STUDY SITES AND POPULATION

a. Study Sites

The evaluation will be conducted nationally in Malawi. Data collected may pertain to the entire national cohort of ART patients (e.g. Baobab Health NART) or to specific smaller cohorts developed by implementing partners, other researchers, and clinics themselves.

b. Inclusion Criteria

This study aims to measure coverage and outcomes of DSD across Malawi. For this reason, we will include in our study all adults who are accessing care for HIV anywhere in the country. The inclusion criteria are shown below.

Inclusion criteria

- ≥ 15 years old
- Patients accessing care for HIV within the data collection period (January 1, 2014 to February 28, 2021)
- In any HIV transmission risk group (general adults and adolescents, high transmission risk populations)

Exclusion criteria

None

Children younger than 15 are excluded from this study for two reasons. First, they are typically treated in pediatric HIV programs that have different drug regimens, visit schedules, and models of care than do adults. Second, the vast majority of DSD implementation in the focus countries to date has involved only adult and adolescent patients, not children [15].

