6. DATA SOURCES AND MANAGEMENT

a. Data Sources

The MOH and its partners will implement the DSD strategies addressed in this study. This protocol is solely for an evaluation of the coverage and outcomes of the interventions. The study team will have no involvement in providing services nor any interaction with patients. The evaluation will instead rely solely on existing, retrospective national-, facility-, and patient-level records.

Routine data sources to be accessed for this study include:

- Baobab Health National ART (NART) System
- Baobab Health Laboratory Information Management Systems (LIMS)
- Other MOH electronic and paper patient records and registers which capture relevant information related to the care and treatment of patients in any model of ART care and treatment. NART does not currently fully capture model of service delivery, for example, so access to paper files at clinics may be required to build the study database.
- Existing, de-identified data sets from trial, cohort, and observational studies, in collaboration with implementers, technical support partners, and research organizations.

The Ministry of Health will be asked to assure and facilitate access to Baobab Health's NART, LIMS and other routinely collected sources of electronic data.

Data will be collected for all patients in each data set who accessed care for HIV on or after January 1, 2014. The focus countries began large-scale implementation of DSD in 2015 or 2016. Starting in 2014

will thus allow us a pre-intervention period for comparison. Data collection will continue throughout the study period, which ends on February 28, 2021.

b. Data Fields to be Collected

Below (Table 1) we summarize the existing data required for the evaluation. A detailed list of data fields follows this summary.

Table 1. Data sought for evaluation of DSD

Themes	Potential availability and source(s)
Proportion of current ART patients meeting definition	Data from electronic medical records, existing M&E reports, IeDEA
of stable; distribution of reasons for not meeting	and PEPFAR partners, cohorts under observation, facilities
definition	participating in others' studies
Geographic distribution and description of	Reports from existing implementers and technical support
differentiated models in use	partners and MOH
Number (proportion) of patients in each model at time	Data from existing implementers and technical support partners,

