of data collection; patient-months enrolled in each	with quality assessment through primary data collection at a
model in previous 12-month period	sample of sites
Location, duration, and frequency of dispensing for	Electronic medical record data; pharmacy data
ARVs and other ART-related medications (e.g. INH)	
Number of facility and non-facility visits per patient	Electronic medical record data
per year, by model of care and purpose of visit (e.g.	
clinical consultation, medication pickup)	
Number and outcomes of viral load tests, CD4 counts,	Electronic medical record data
and other ART-related laboratory assays per patient	
per year, by model of care	

The specific data fields available and required for different patient types will vary slightly (e.g. viral loads will not be available for patients newly initiating treatment). In general, however, we will collect a common set of variables for all patients. The specific fields are listed below:

Demographic information

- Electronic medical record system number (e.g. Baobab Health NART record number)*
- Clinic file, register, and card numbers (assigned by the clinic)*
- National ID number*
- Name*
- Date of birth*
- Weight and height or BMI
- Sex
- Age in years
- Marital status if recorded
- Employment status if recorded
- Education level if recorded

· Smoking and alcohol use if recorded

*Identifiers like name and date of birth are required to link electronic and paper-based records pertaining to individual patients. Many clinics use name or initials and date of birth to create a clinic record number. For example, numbers and dates of clinic visits can typically be extracted from Baobab Health, but the specific model of care used by an individual patient may require linking Baobab Health records to data manually transcribed from paper clinic records.

Clinical information

- Date of positive HIV test (if available)
- Dates of all clinic visits (including pre-ART and after ART initiation)
- Primary purpose of all clinic visits (e.g. HIV test, CD4 count, counselling, ARV dispensing, ART monitoring, etc.)
- Dates of next scheduled clinic visits (dates patients are expected to return to clinic)
- Date treatment eligibility determined, if reported
- Date and result of CD4 count indicating treatment eligibility (baseline)
- WHO stage and clinical conditions
- Date and result of TB symptom screen
- Date, type, and result of TB test
- Date TB treatment initiated, if relevant

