7. DATA ANALYSIS

a. Sample Size

In order to measure national coverage of DSD, we will access data for up to the entire national ART cohort. In Malawi, the estimated number of individuals on ART is currently 740,000 [16]. This is expected to increase to \geq 90% of the entire HIV-infected population by the time the study ends. We therefore expect to collect and analyze data for up to 1,000,000 individuals, the estimated HIV-positive population in Malawi [16]. As noted above, all data will be drawn from records that exist at the time of data collection; the study will have no interaction with study subjects.

b. Outcomes

To estimate uptake, benefits, and costs of DSD, we will aim to report the following results, stratified by model care and/or other patient or clinic/model characteristics:

- Percentage of current ART patients eligible for any alternative model, under current guidelines
- 2. Demographic, economic, and clinical characteristics of patients in each model, as data allow.
- 3. Patient-months enrolled in any DSD and in each model
- 4. Frequency of transfer between models of care, including back to the conventional model
- 5. Location, duration, and frequency of ARV dispensing
- 6. Number of clinical visits/patient/year
- 7. Quantities of resources used/patient/year
- 8. Geographic distribution of patients enrolled in each DSD
- 9. Retention on ART, measured at 6-month intervals
- 10. Proportion virally suppressed (< 400 copies/ml³)
- 11. Other outcomes relevant to DSD that can be estimated from available data

Note: as this is not a clinical trial, we have not designated primary and secondary outcomes. We will report as many of the above outcomes as data allow.

c. Analysis

To evaluate the broad, national- or system-wide implications of differentiated models of ART delivery in the context of health systems in sub-Saharan Africa, we will conduct the following analyses.

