Outcomes 9-11 measure health outcomes by model of care. For these outcomes, we will begin with descriptive analyses of the characteristics of the population stratified by model of care. For each outcome described above, we will conduct a crude analysis comparing the proportion of subjects with the outcome by model of care. Next, we will conduct an analysis for each outcome accounting only for clustering using generalized estimating equations (GEE) with an unstructured correlation matrix and clustering by treatment site. In all cases the outcomes are dichotomous and therefore we will calculate risk differences comparing the intervention to the comparison arms using a linear link function and a binomial distribution. Next, should any imbalances between models of care be detected, we will adjust for those covariates in our GEE model. Finally, we will look for differences in the effects of the models of care by important baseline characteristics (e.g. size of the treatment population, rural vs. urban, province, etc.) using stratified analyses.

d. Dissemination of Findings

The results of this study will be disseminated as widely as possible in the study countries and globally. A full report will be made to local stakeholders and will be circulated widely and posted on our website. We will also develop a short briefing document to send to the Ministry of Health, donor agencies, and other interested organizations, and we will present the results at relevant conferences domestically and internationally. One or more journal manuscripts will be submitted to an appropriate peer-reviewed international journal.

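### Retention on ART is compared between models of care, but the extraction list holds no death, transfer-out or stop status, and potential follow-up differs by model with no rule for it

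*Protocol*

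**What the plan says.** Outcome 9 in Protocol Section 7b is "Retention on ART, measured at 6-month intervals". For Outcomes 9-11, Section 7c starts with a crude analysis "comparing the proportion of subjects with the outcome by model of care". It then moves to GEE models clustered by treatment site, with a binomial distribution and a linear link: "In all cases the outcomes are dichotomous and therefore we will calculate risk differences comparing the intervention to the comparison arms".

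The population in Section 5b is "Patients accessing care for HIV within the data collection period (January 1, 2014 to February 28, 2021"), with no minimum follow-up. Section 6a closes the data on the same day: "Data collection will continue throughout the study period, which ends on February 28, 2021". It also says "The focus countries began large-scale implementation of DSD in 2015 or 2016".

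Section 6b sets out the specific fields and states "we will collect a common set of variables for all patients". The clinical list covers visit dates, next scheduled visits, ART start, regimen changes, drug collections with their duration, viral loads and other laboratory results. The DSD list covers the model and how long the patient was enrolled in it. Neither list has death, transfer-out to another facility, stopping of ART, or a date for any of these. The only patient transfer in the plan is the move between models of care (Outcome 4).

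**The concern.** A patient who moves to another facility and stays on treatment is retained on ART, but leaves the same trace in the originating clinic's visit and dispensing dates as a patient who is lost. Without a recorded status the analysis cannot separate the two unless the patient reappears in another linked source. If unrecovered transfers are more common in one model, the risk difference moves for a reason unrelated to retention.

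Potential follow-up is a second, separate matter. With rolling entry up to the closing date, recent entrants have no k-month result, and their share is larger where entry began later. The protocol gives no rule for who belongs in the denominator at each interval.

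Section 3b expects little room for short-term gains in health outcomes but says long-term retention may be affected. Retention is therefore where a health effect is most expected, and late time points are where follow-up is scarcest. With up to 1,000,000 records (Section 7a), confidence intervals may be narrow and would not reveal a systematic error.

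**Working it through.** The protocol states no retention, transfer or attrition rate, so there is no figure of its own to reproduce.

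**1. Potential follow-up**

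Inputs: data start 1 January 2014 and closure 28 February 2021 (Sections 5b and 6a); large-scale DSD from 2015 or 2016 (Section 6a). Assumption: index dates are spread evenly from the start date to closure.

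With M the months from start to closure (days / 30.4375), the share lacking k months is k / M.

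| Entry from | M | under 6 months | under 12 months | under 24 months |
|---|---|---|---|---|
| Jan 2014 | 2615 / 30.4375 = 85.9 | 6/85.9 = 7.0% | 12/85.9 = 14.0% | 24/85.9 = 27.9% |
| Jan 2015 | 2250 / 30.4375 = 73.9 | 6/73.9 = 8.1% | 12/73.9 = 16.2% | 24/73.9 = 32.5% |
| Jan 2016 | 1885 / 30.4375 = 61.9 | 6/61.9 = 9.7% | 12/61.9 = 19.4% | 24/61.9 = 38.8% |

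These are shares without a possible result, not biases. Growing enrolment would raise them; a large block of patients already in care in January 2014 would lower the first row.

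They become bias only if such patients are counted as not retained, which the protocol does not say. If they were, with equal true 12-month retention R = 90% in both groups (assumed):

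- Spurious difference = R × (12/M_conventional − 12/M_alternative).
- DSD from January 2015: 0.90 × (14.0% − 16.2%) = −2.0 points.
- DSD from January 2016: 0.90 × (14.0% − 19.4%) = −4.9 points.
- With each denominator limited to patients with 12 months available (index date by 28 February 2020), or with censoring at closure, this component is 0.

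**2. Transfer-out**

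Let q be the share of patients whose transfer is not recovered by linkage and is counted as loss. With equal true retention R:

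- Spurious difference = R × (q_conventional − q_alternative).
- At R = 90% (assumed), each percentage point of difference in q moves the risk difference by 0.9 points, in favour of the model with fewer unrecovered transfers.
- Equal q gives 0.

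No value of q can be taken from the protocol.

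**3. Can it be repaired later?**

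A denominator rule can be set at analysis, because it needs only dates. A status that was not extracted cannot. Section 6c has paper records transcribed on site onto electronic forms, and Sections 6c and 8i destroy the linking files once linkage is complete. After that, a missing status can hardly be added for individual patients.

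**The case against.** The strongest reply is that little here is an error as such. Retained or not at a fixed time is a sound dichotomy among patients observable to that time. Nothing in Sections 7b or 7c counts short follow-up as failure, and a denominator rule is commonly left to the SAP, which is not shown. Section 6c collects national ID, name, date of birth and record number for linkage, and Section 5a allows national cohort data, so many transferred patients may reappear elsewhere. Death and stopping both ordinarily count as not retained, so failing to separate them from loss does not by itself bias the difference. No outcome is designated primary, and status can be taken only where it is recorded.

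Most of this stands and narrows the point. What remains is transfer-out beyond the linked data, and the fact that the list itself omits the status. Data sets shared in bulk may happen to contain it, but the plan does not ask for it.

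A reader might go further and infer three things that the protocol does not support:

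- That a dichotomous analysis of retention is wrong in itself. It is not, once the denominator is limited.
- That longer refills make patients in alternative models look retained for longer. The protocol states no definition of loss to which this would apply, and it already collects scheduled visits and dispensed duration. Dating loss from the end of supply would not remove the effect in any case.
- That transfers produce a bias of a known number of points against conventional care. Any such figure comes from assumed transfer rates.

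**Conclusion.** The point holds as an inexpensive improvement. The Section 6b list omits ART outcome status and date, although retention is compared between models, and transfers outside the linked data cannot then be told from loss. This can bias the risk difference if transfer rates differ by model; size and direction are unknown.

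On the protocol's own dates, potential follow-up also differs by model. Under uniform entry, 14.0% of patients lack 12 months with entry from January 2014, against 16.2% to 19.4% with entry from January 2015 or January 2016. Whether that biases anything depends on a denominator rule that the protocol does not give. The two mechanisms need not act in the same direction, and no net effect can be stated.

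**What to change.** **Section 6b:** add ART outcome status (died, transferred out to another facility, stopped) and its date, where recorded, before extraction begins and before any linking file is destroyed.

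**Section 7c:** limit each k-month retention proportion to patients whose index date is at least k months, plus any grace period, before data closure. Without a grace period the last index dates are 28 August 2020, 28 February 2020 and 28 February 2019 for 6, 12 and 24 months. Alternatively, use Kaplan-Meier or Aalen-Johansen estimates censored at closure. Treat documented transfers as censored rather than lost, with sensitivity analyses that count them all as lost and all as retained. The risk difference may remain the reported measure.

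**Cost:** one extra field group in the extraction and a short rule in the analysis text. Status will be incomplete where clinics do not record it. With restricted denominators, recent entrants add nothing to late time points.

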In the published literature and conference presentations, calls for funding proposals, and MOH documents, DSD are assumed to generate a wide range of potential benefits. These include better access to and outcomes of treatment, increased clinic capacity and lower costs for providers, lower costs for patients, and better quality and greater satisfaction for both providers and patients. Despite a high level of confidence on the part of DSD advocates, ministries of health, funders, and implementing partners that at least some of these benefits must materialize, there is in fact very little evidence to support these assumptions. Published research to date has suggested modest or minimal improvement in health outcomes and small reductions (if any) in per-patient provider costs. We note that there is little room for short-term improvement in health outcomes, as most patients enrolled in alternative models to date have been virally suppressed at entry, but DSD may certainly affect long-term retention in care. We also expect only modest potential for per-patient out-of-pocket cost reductions, due in part to the large share of costs attributable to medications[11-13]. We have found no published evidence that moving HIV patients into alternative models increases the quality or quantity of services that clinics provide to conventional-model patients or patients with non-HIV conditions.

Fortunately, in the past half-decade, substantial groundwork has been laid for standardizing methods for evaluating the performance of DSD at the patient level. We are thus at a point in time at which many alternative models are already being implemented and some evaluated, and an initial set of evaluation indicators has been published[14]. With some micro-data in hand, but little "macro" evidence of overall scale, impact, costs, and benefits, this is therefore an apt time to launch a big picture analysis of DSD, to help guide ministries of health, donor agencies, and others to make better decisions about what to scale up, where, and for whom.

c. Objective

The objective of this study is to analyze existing data sets with data relevant to differentiated service delivery for HIV treatment in Zambia, Malawi, and South Africa. This protocol is solely for the analysis of existing data; the study contains no interaction with patients, providers, or other individuals.

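### The identity-link binomial GEE fixed for Outcomes 9–11 may fail to converge, or give fitted probabilities outside 0–1, once covariates are added

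*Protocol*

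**What the plan says.** Protocol section 7c (Analysis) sets out a sequence for Outcomes 9–11: description by model of care, a crude comparison, a clustering-only analysis, then adjustment. The clustering step uses "generalized estimating equations (GEE) with an unstructured correlation matrix and clustering by treatment site". All outcomes in this group are treated as dichotomous, and the effect measure is the risk difference, obtained "using a linear link function and a binomial distribution". A linear link here is the identity link.

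Adjustment stays in this model: "should any imbalances between models of care be detected, we will adjust for those covariates in our GEE model". The protocol names no other link or distribution for the adjusted step.

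The named outcomes in section 7b are "Retention on ART, measured at 6-month intervals" and "Proportion virally suppressed". No expected proportion is given for either. Section 3b (Rationale) describes the level only in words: "there is little room for short-term improvement in health outcomes", because "most patients enrolled in alternative models to date have been virally suppressed at entry".

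**The concern.** In an identity-link model the fitted probability is a plain sum of coefficients times covariates, and nothing keeps it between 0 and 1. The binomial variance, which sets the weights in the estimating equations, is p(1−p). It is zero at p = 1 and negative beyond. If any patient's fitted value crosses the boundary, the fit can break down. If the software truncates fitted values, it may report convergence and hide the problem.

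With model of care as the only predictor, the fitted values are simply group proportions and the fit is safe. The difficulty comes with the covariates. Adjustment is likely to be called for: the alternative models have mainly been offered to stable patients (sections 3a and 3b), so groups differ by selection, and with up to 1,000,000 records (section 7a) imbalances will be found.

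The adjusted risk difference, as specified, may therefore be unobtainable. The analyst would then have to change the model, or change how covariates are coded or which are kept, after seeing the data.

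**Working it through.** The protocol states no figure to reproduce, so the check is a derivation followed by simulation.

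**1. Mechanism.** Model: p = β₀ + β₁·(model of care) + Σγₖxₖ, with variance p(1−p) and weight 1/[p(1−p)]. At a fitted value of 1.02, for example, the variance is 1.02 × (−0.02) = −0.0204, so the weight is negative.

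**2. How soon the boundary is reached.** Assume four independent standardised continuous covariates with log-odds 0.5, 0.4, 0.3 and 0.3. The SD of their combined effect on the logit scale is s = √(0.25 + 0.16 + 0.09 + 0.09) = √0.59 = 0.768. On the probability scale, the fitted values have SD of about p(1−p)s. The distance from the mean p up to 1 is 1−p, which in SDs is (1−p)/[p(1−p)s] = 1/(ps).

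- p = 0.70: 1/(0.70 × 0.768) = 1.86 SD, a normal tail of about 3.1%. Least squares in the simulation put 2.8% of fitted values outside 0–1.
- p = 0.98: 1/(0.98 × 0.768) = 1.33 SD, a tail of about 9.2%. The simulation gave 11.2%.

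Moving from 0.70 to 0.98 shortens the distance only from 1.86 to 1.33 SD. For continuous covariates, then, a high outcome proportion is not the main driver.

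**3. Simulation.** Assumptions: 5,000 patients per data set, 100 data sets per cell, logistic truth, treatment log-odds 0.3, and the covariate effects above or half of them. The identity-link binomial model was fitted by iteratively reweighted least squares. A fit failed if any fitted probability left 0–1 during iteration or if it did not converge. Failures per 100:

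| Covariates | 0.70 | 0.80 | 0.90 | 0.95 | 0.98 |
|---|---|---|---|---|---|
| 4 continuous, full effect | 100 | 100 | 100 | 100 | 100 |
| 4 continuous, half effect | 77 | 98 | 99 | 99 | 97 |
| 4 binary, full effect | 0 | 0 | 18 | 37 | 69 |
| 4 binary, half effect | 0 | 0 | 0 | 0 | 9 |
| 1 binary, full or half effect | 0 | 0 | 0 | 0 | 0 |

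**4. With GEE.** Assumptions: 50 sites of 100 patients, exchangeable working correlation, 60 data sets per cell. With four continuous covariates, 60 of 60 did not converge at each of the five levels. With four binary covariates at 0.70, 60 of 60 converged with no fitted value outside 0–1. The unstructured matrix was not simulated; it is a separate matter.

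**5. Bounded covariates.** With age and time on ART confined to plausible ranges, 5,000 patients and clustering ignored in fitting, 35 to 40 of 40 fits failed at effects of 0.3 log-odds per SD or more (levels 0.70–0.95), and 0 to 13 of 40 at 0.15. With covariates categorised, none failed at weak effects and up to 34 of 40 at strong ones.

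**6. Sample size.** A similar set-up used bounded age and time on ART plus sex, with 30 data sets per cell. At 0.2 log-odds per SD, failures at n = 2,000, 20,000 and 200,000 were 14, 22 and 30 (level 0.80), 14, 30 and 30 (0.90), and 23, 27 and 30 (0.95). At 0.15 and n = 200,000 they were 1, 26 and 30 across those levels. At 0.1 there were none.

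**7. Alternatives.** In step 4, a logistic model standardised to a risk difference fitted every data set, with absolute mean error below 0.002. In step 3, least squares (identity link, constant variance) had absolute mean error of at most about 0.002, but 0–11% of its fitted values lay outside 0–1.

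**The case against.** An identity-link binomial model is a legitimate and direct route to a risk difference, and it often fits. With one binary covariate, or four weak ones up to 0.95, every simulated fit converged. The protocol does not say that covariates enter linearly. Its list with age, time on ART and baseline CD4 is given for Outcomes 1–4, so carrying it to Outcomes 9–11 is an assumption. Covariate coding and a fallback for non-convergence are ordinary SAP content, and the SAP is not shown. Failure rates also depend on software, starting values, covariate prevalence and effect size. All of this stands, and it limits the point to a risk.

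A reader might infer that the protocol expects these outcomes to be near 100%. It does not say so. The remark in section 3b is about short-term change and suppression at entry to alternative models, and the same sentence allows that long-term retention may be affected. Retention is Outcome 9, and the study population also includes conventional-model patients.

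A reader might also infer that the adjusted analysis is declared to be the main one. Section 7c ranks none of its analyses, and section 7b designates no primary outcome. Nor do the documents show that analysts would drop covariates; that is only one possible response to a failed fit.

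Two defences do not hold. The statement in section 7c that regression is not the primary analysis concerns Outcomes 1–4. And a large sample does not rescue the model: beyond quite weak effects, failures rose with sample size.

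**Conclusion.** The point holds as a weakness in a method the protocol itself fixes, not as a complaint about a missing fallback. After adjustment, the identity-link binomial GEE may fail to converge or give fitted probabilities outside 0–1. With moderate continuous covariates entered linearly, failure was the usual result at assumed levels from 0.70 up. With several strong categorical covariates, it became common as the proportion rose. With one or a few weak categorical covariates, the model usually fits.

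The stronger statement, that the model fails whenever covariates are added, is not supported. The outcome levels, covariate effects and covariate form are all assumptions, because the protocol gives no suppression or retention percentage. The simulations used independent data or an exchangeable correlation, and a strict failure criterion. The crude and clustering-only analyses are not affected by this mechanism.

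**What to change.** For the adjusted analysis of Outcomes 9–11, replace the identity-link binomial with a logistic-link GEE with site-clustered robust variance, and obtain the risk difference by marginal standardisation. That is, average each patient's predicted probability under each model of care over the study population and take the difference. Fitted probabilities then stay within 0–1, and both the risk-difference scale and the clustering by site are kept. The cost is one line of wording and one extra standardisation step, with a standard error that respects the clustering.

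An acceptable alternative is an identity link with constant working variance and site-clustered robust errors. It removes the undefined variance and fits reliably, at a slight loss of efficiency. It does not keep fitted values within 0–1. In a check with 40 sites of 60 patients and log-odds of 0.4 for standardised age and time on ART, every one of 100 data sets had some out-of-range values at both 80% and 95%. With log-odds of 0.2, 76 and 83 of 100 did. It should therefore be chosen for stability, not for valid individual probabilities. Whichever is chosen should be named before the outcome data are analysed.
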